9.1.2 Randomization

Participants will be randomized 1:1, without stratification, in block sizes of 4.

9.1.3 Accrual Estimates

We estimate an enrollment rate of 1-2 participants per month, for an enrollment period lasting 6 months. It is expected that approximately 50% of patients being referred to the study will meet eligibility criteria at the time of screening. The study team thus aims to screen approximately 24 or more potential participants.

Pilot Study - Ketamine Page 40 of 55

9.2 Analyses Plans

9.2.1 Population for Analysis

Descriptive analyses will be prepared based on the Modified Intention-to-Treat study populations, including all participants who received a dose of either oral or intramuscular ketamine on Day 0 (at 0.5 mg/kg).

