Secondary Objectives	 To characterize the preliminary safety and tolerability of K-MaP in demoralized patients with stage 3 and 4 GI cancers. To assess the magnitude and durability of improvement from randomization in psychosocial distress. To assess the magnitude and durability of improvement from randomization in pain. To assess the magnitude of change from randomization in opioid analgesic use. To assess the magnitude and durability of change from randomization in interoceptive awareness. 							
Sample Size	12 patients, 6 patients per arm. Arm A: (0.5 mg/kg of ketamine, PO) Arm B: (0.5 mg/kg of ketamine, IM)							
Duration of Study Treatment	Ketamine will be given once on Day 0/Visit 4. Patients will receive MaP therapy 4 times, twice before ketamine administration (Day 0), and twice afterward: 1. Day -13 to -4/Visit 2 2. Day -12 to -1/Visit 3 3. Day 3 (+/- 2 days)/Visit 5 4. Day 11 (+/-2 days)/Visit 7 The duration of treatment for K-MaP therapy (ketamine and MaP) is approximately up to 28 days.							
Duration of Follow up	Patients will be followed up to 35 days (+/-2 days) after ketamine administration.							

Pilot Study - Ketamine Page 4 of 55

Study Schema

Pilot Study - Ketamine Page 5 of 55

List of Abbreviations

AE adverse event

ALP alkaline phosphatase

ALT alanine aminotransferase
AST aspartate aminotransferase

BMP Basic Metabolic Panel

BPI-SF Brief Pain Inventory-Short Form

BUN blood urea nitrogen

CBC complete blood cell (count)

CEQ Challenging Experience Questionnaire

CMP Comprehensive Metabolic Panel

CNS central nervous system

CR complete response

CRF case report form

C-SSRS Columbia Suicidality Severity Rating Scale

CT computerized tomography

CTCAE Common Terminology Criteria for Adverse Events

CTMS Clinical Trial Management System

DFS disease-free survival
DLT Dose-limiting toxicity
DS-II Demoralization Scale II

DSMC Data and Safety Monitoring Committee

DSMP Data and Safety Monitoring Plan

ECG/EKG electrocardiogram

ECOG Eastern Cooperative Oncology Group

FACIT- Functional Assessment of Chronic Illness Therapy Palliative Care 14 Item Version

Pal-14

FDA Food and Drug Administration

FDG Fluorodeoxyglucose

GAD7 General Anxiety Disorder-7

GCP Good Clinical Practice
GFR glomerular filtration rate

HBsAb hepatitis B surface antibody HBsAg hepatitis B surface antigen HBcAb hepatitis B core antibody

HC Ab hepatitis C antibody

Pilot Study - Ketamine Page 6 of 55

List of Abbreviations

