3.8 Randomization Procedures

A total of 12 patients will be randomized on Day 0 at a 1:1 ratio to receive either 0.5 mg/kg of oral ketamine, or 0.5 mg/kg of IM ketamine. Randomization will be in block sizes of 4.

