The participant will be randomized to ingest liquid ketamine 0.5mg/kg vs. an equivalent mL quantity of normal saline (placebo) mixed with cranberry juice (prepared by unblinded study staff) in a medication administration room located next door to the treatment room. At 10 minutes following oral ingestion of cranberry juice, while sitting in a wheelchair in the medication administration room, all participants will be administered an intramuscular injection (also prepared by unblinded study staff). The injection will be administered either by an RN, NP, or MD/DO involved in the study. Participants who received oral ketamine 0.5mg/kg will be administered normal saline via IM injection while those who received normal saline (placebo) in cranberry juice will receive ketamine 0.5 mg/kg IM. Following this injection, the participant (still in a wheelchair) will be rolled into the treatment room located across the hall from the medication administration room, where they will be supported by the therapy facilitators in transferring from the wheelchair to the couch and instructed to lie down wearing eyeshades and listening to a preselected music playlist via headphones or speakers. The participant will be instructed to focus their attention internally and to attempt to interact minimally with the two facilitators present in the room throughout the drug session. The facilitators will be as nondirective as possible in their interactions with the participant. In the event of a psychologically challenging experience such as significant anxiety or confusion, the facilitators will provide verbal reassurance and, when consented to prior to the session, supportive touch (e.g., brief handholding or hand-on-shoulder). Participants will have been instructed in the preparatory therapy session to notify the study therapists if during the treatment they feel anxiety or fear.

Facilitators will work in dyads (one Lead Facilitator and one Assistant Facilitator) and have licensure or clinical experience according to the following requirements, which the FDA has used for prior studies of medication-assisted talk therapy:

Lead Facilitator: Licensed to provide healthcare with professional training and clinical experience in psychotherapy. They must be licensed to practice independently. Acceptable professional credentials are limited to the following: clinical or counseling psychologist (PhD or PsyD), psychiatrist or other

Pilot Study - Ketamine Page 25 of 55

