7.4 Evaluation of Safety

The safety parameters for this study include all laboratory tests, physical findings, and spontaneous reports of adverse events reported to the investigator by participants.

Safety will be assessed according to the NCI CTCAE version 5.0.

Safety analyses will be performed for all participants who receive ketamine treatment in the trial (V2).

8 Safety Parameters

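### The modified ITT set requires receipt of ketamine, which comes first in the oral arm and second in the IM arm, so a participant who stops between the two blinded steps is excluded from the IM arm only

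*Combined protocol and SAP*

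**What the plan says.** Section 3.8: "A total of 12 patients will be randomized on Day 0 at a 1:1 ratio". The abstract gives "12 patients, 6 patients per arm", and section 9.1.2 adds: "Participants will be randomized 1:1, without stratification, in block sizes of 4".

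Section 5 describes administration in two blinded steps. Everyone drinks cranberry juice containing either ketamine or saline. The injection follows: "At 10 minutes following oral ingestion of cranberry juice". On the contents of the injection in the oral arm, section 5 says "Participants who received oral ketamine 0.5mg/kg will be administered normal saline via IM injection". For the IM arm it gives the reverse order: "those who received normal saline (placebo) in cranberry juice will receive ketamine 0.5 mg/kg IM". Sections 3.1 and 5.1 give the same order.

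Section 9.2.1 bases the descriptive analyses on a modified intention-to-treat population, "including all participants who received a dose of either oral or intramuscular ketamine on Day 0 (at 0.5 mg/kg". Section 7.4 sets a similar condition for safety: "Safety analyses will be performed for all participants who receive ketamine treatment in the trial (V2". (The visit label there does not match the study calendar, which puts ketamine at Visit 4.)

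Section 6 lets an unwilling participant stop at any time except while under the acute effects of ketamine. Nowhere do the documents say how to classify a randomized participant who takes the drink but not the injection.

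**The concern.** A modified ITT rule that excludes undosed participants is normally harmless when dosing is a single blinded act, because the rule then works the same way in both arms. Here it does not. The condition is met at the first step in one arm and only at the second step in the other. For anyone who stops in the 10 minutes between, membership of the analysis set depends on the assigned arm alone. That is a post-randomization exclusion that can operate in one arm only.

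What is at stake is the comparison of the arms in section 9.2.3: the mean DS-II trends by arm, the between-arm ANCOVA estimates (including the Day 35 difference with its 95% CI) and Cohen's d. With six per arm, one participant carries a sixth of the arm's weight.

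**Working it through.** **The plan's own figure.** 12 participants / block size 4 = 3 complete blocks. At 1:1, each block gives 2 per arm, so 3 × 2 = 6 per arm. This agrees with the stated 6 and 6.

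**Membership by stopping point** (order of administration from section 5, set rule from section 9.2.1):

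| Participant stops | Oral arm | IM arm |
|---|---|---|
| before the drink | no ketamine: excluded | no ketamine: excluded |
| after the drink, before the injection | ketamine taken: kept | saline only: excluded |
| after the injection | kept | kept |

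Only the middle row differs by arm. It follows from the wording and needs no outside assumption.

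**How often.** The documents give no stopping rate, so let q be an assumed chance, equal in both arms, that a participant stops between the steps. The chance that the rule removes at least one of six IM participants is 1 − (1 − q)^6, and the expected number removed is 6q.

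| q (assumed) | Chance of at least one IM exclusion | Expected IM exclusions | Oral exclusions |
|---|---|---|---|
| 1% | 1 − 0.99^6 = 5.9% | 0.06 | 0 |
| 2% | 1 − 0.98^6 = 11.4% | 0.12 | 0 |
| 5% | 1 − 0.95^6 = 26.5% | 0.30 | 0 |
| 10% | 1 − 0.90^6 = 46.9% | 0.60 | 0 |

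**What one case does.** It removes 1/6 = 16.7% of the IM arm and none of the oral arm.

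**Effect on DS-II means (illustrative).** Suppose one participant in each arm stops between the steps and has no later data, and the other five in each arm improve by 2 points. Section 9.2.3 fills missing values with the baseline observation, so a stopper who is in the set counts as zero change.

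- Oral arm under the current rule: (5 × 2 + 0)/6 = 1.67 points.
- IM arm under the current rule: (5 × 2)/5 = 2.00 points.
- Apparent difference from identical behaviour and identical outcomes: 2.00 − 1.67 = 0.33 points.

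**With the set defined by starting the drink.** One stop per arm gives 6 oral and 6 IM analysed, instead of 6 and 5, and both means are 1.67. Two stops per arm give 6 and 6 instead of 6 and 4.

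**The case against.** The strongest reply is that the event is close to hypothetical. The window is 10 minutes. Vital signs are scheduled before the drink and then at 30 minutes, so no scheduled check falls inside it. The blood-pressure hold in section 5 applies before study drug is given. Participants must be willing to follow study procedures, and those with intractable nausea or vomiting are excluded. Section 9.1.1 plans no formal efficacy tests, and its go-forward rule is judged within each arm, a question that a set of exposed participants suits. A stopper who leaves the study would add only carried-forward baseline values. All of this stands, and it limits the weight of the point. It does not remove the arm-dependent rule, which acts on the between-arm estimates that section 9.2.3 does plan.

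Three stronger readings are tempting and are not supported.

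- *IM would look better tolerated, or more feasible, because its refusers vanish.* A reader might infer, for example, that four IM completers would be reported as 4/5 = 80% and not 4/6 = 67%, which straddles the 75% criterion in section 9.2.2. But section 2.2 sets the completion endpoint among enrolled participants by arm, so an IM refuser stays in the denominator and counts as a failure. The tolerability criterion is zero treatment-related serious adverse events, and someone who drank only saline says nothing about IM ketamine.
- *Completion should require both blinded steps.* That would fail an oral participant who took ketamine and missed only a saline injection, which is a poorer measure of receiving the intervention.
- *The safety set needs the same redefinition.* Adding an unexposed participant to the IM denominator would dilute IM event rates. Nor are such events lost to oversight: the study calendar collects adverse events from Visit 2 onward, and serious ones go to the monitoring committee.

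It might also be assumed that vomiting after the drink triggers the exclusion. Nothing in the documents says that vomiting cancels the injection.

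**Conclusion.** The point holds for the analysis set in section 9.2.1. As written, the rule gives opposite membership to two participants who make the same blinded decision, and no other section repairs it. The asymmetry follows directly from the order of administration. Its frequency does not: every probability above rests on an assumed q, taken as equal between arms and independent between participants, and the expected number affected is at most 0.6 IM participants over the range shown. The 0.33-point shift is an illustration that assumes one stop per arm, no follow-up data and a 2-point gain in the rest.

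This is a low-probability flaw whose effect would be noticeable at six per arm. It concerns the by-arm DS-II means and the ANCOVA estimates. It does not undermine the feasibility endpoint or the tolerability criterion. It is worth correcting because the correction is cheap now, and a choice made after unblinding would be hard to defend.

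**What to change.** In section 9.2.1, define the modified ITT set as all randomized participants who began blinded study-drug administration, meaning that they drank any of the oral solution, analysed in the arm to which they were randomized. List anyone who received only one of the two steps.

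Keep the completion endpoint in sections 2.2 and 9.2.2 as receipt of ketamine among enrolled participants. Keep the safety summary in section 7.4 by actual ketamine exposure, and list separately any adverse event in a randomized participant who began administration but received no ketamine. The visit label in section 7.4 can be reconciled with the study calendar in the same edit.

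The cost is a reworded definition and a listing in section 9.2.1 and one added sentence in section 7.4, with no new data or procedures. The downside is that an IM participant who received no ketamine slightly dilutes that arm's estimate, possibly through carried-forward values alone. The listing makes this visible.

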9.2.2 Primary Analysis (or Analysis of Primary Endpoints)

The primary objective of this pilot study is to assess the feasibility and preliminary safety of administering Meaning and Purpose therapy combined with oral vs. intramuscular ketamine (K-MaP) in demoralized patients with stage 3 or 4 GI cancers (i.e., pancreatic, colorectal, hepatocellular, biliary, or gastro-esophageal). Pre-determined criteria for success of feasibility include:

- A recruitment rate of 50% among referred/screened participants and those ultimately found to be fully eligible and enrolled in the study.
- Completion rates of (i) 75% for participation in 4 Meaning and Purpose therapy sessions and (ii) 80% of 5 on-study DS-II assessments (Visits 1, 4, 6, 8, and 9), in addition to receipt of ketamine.
- Qualitative assessment of clinician fidelity to manualized K-MaP intervention.
- Qualitative assessment of acceptability of the intervention and assessments by participants at the end of the study, with at least 60% of included participants completing this assessment.

9.2.3 Secondary Analysis (or Analysis of Secondary Endpoints)

Secondary Objective #1: To characterize the preliminary safety and tolerability of K-MaP in patients with stage 3 or 4 Gl cancers (i.e., pancreatic, colorectal, hepatocellular, biliary, or gastro-esophageal), we will analyze:

- Rates and types of adverse events (AEs), unexpected AEs, and serious AEs will be summarized by arm. Pre-determined criteria for assessment of tolerability to K-MaP include zero treatment-related serious adverse events.
- Across each study arm, changes in individual participant and mean heart rate (HR), systolic (SBP) and diastolic blood pressure (SBP) measurements from 10 minutes prior to ingestion of the oral solution to 30, 60, 90, 120, and 180 minutes post-oral ingestion, using random effects models that account for correlated outcomes within participants. The below thresholds will be used as indications of potential concern for patient safety. These estimates have been determined on the basis of established human safety thresholds and findings from a recent meta-analysis of hemodynamic responses to sub-anesthetic ketamine doses in patients with psychiatric conditions.[109]
 - An increase in HR baseline of greater than 25 BPM in any patient
 - o An increase in SBP of greater than 40 mm Hg in any patient
 - o An increase in DBP of greater than 25 mm Hg in any patient

Pilot Study - Ketamine Page 41 of 55

 Mean CEQ scores on the day of ketamine administration will be compared between the two study arms using ANCOVA models, discussed in the next objective.

Secondary Objective #2: To assess the magnitude and durability of improvement from randomization in psychosocial distress associated with K-MaP, we will measure mean trends in patient-reported outcomes (DS-II, PHQ9, GAD7, FACIT-PAL-14 scores) in each study arm from baseline visit (Day -28 to -7) to post-ketamine (on Days 7, 14, and 35). In addition, we will calculate the proportion of participants per arm who no longer meet criteria for moderate-to-severe demoralization (i.e., DS-II > 10) post-ketamine. We will also measure mean trends in clinician-rated outcomes (CGI-S, DI, and GRID-HAMD-6 scores) per arm as above. ANCOVA models of follow-up endpoints as a function of study arm, adjusted for endpoints at baseline and randomization, will be conducted [110]. ANCOVA results will be presented graphically via mean trends per arm overlaid on individual trends, and via the mean (95% CI) difference between arms at Day 35. Cohen's d will be calculated at each follow-up time to estimate effect sizes. Any missing data will be estimated through the use of single imputation with baseline observations carried forward.

Secondary Objective #3: We will evaluate BPI-SF scores analogously to DS-II scores.

Secondary Objective #4: We will evaluate opioid analgesia use analogously to DS-II scores.

Secondary Objective #5: We will be using pair t-tests to measure mean changes in MAIA-2 scores in each study arm from prior to ketamine administration (on Day 0) to post-ketamine (on Day 7).

Secondary Objective #6: To assess how participants' subjective experiences with ketamine may be related to clinical outcomes, subjective reports of each participant's ketamine experience (videorecorded from Day 0) will be transcribed, inductively coded, and qualitatively analyzed to identify phenomenological content. In addition, participant MEQ and CEQ scores, which provide summary measures of the intensity of ketamine's acute effects, will be evaluated for potential correlation with trends in DS-II, BPI-SF, and opioid use.

Secondary Objective #7: To assess how participants' changes in measures of cardiac interoceptive accuracy may be related to subjective experiences with ketamine, we will assess for correlations between changes in scores on the Heartbeat Detection (HBD) task following the receipt of ketamine (measured pre- and post-dosing on Day 0) and MEQ scores (measured post-dosing on Day 0). We will also evaluate for potential correlation of changes in HBD task scores following receipt of ketamine with post-intervention trends in MAIA-2, DS-II, BPI-SF, and opioid use.

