2.1 Hypothesis

We hypothesize that K-MaP therapy is safe and feasible for administration to patients with advanced GI cancers with moderate-to-severe demoralization. In addition, we hypothesize that stage 3 and 4 GI cancer patients will tolerate K-MaP therapy, and patient experiences during K-MaP therapy may result in improvements from randomization in measures of psychosocial distress, pain, opioid analgesic use, and interoceptive awareness.

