2.3 Secondary Objectives and Endpoints

Secondary Objective	Endpoint(s)	Time Frame

Pilot Study - Ketamine Page 15 of 55

1.	To characterize the preliminary safety and tolerability of K-MaP in patients with stage 3 and 4 GI cancers.	 Adverse events (AEs), Unexpected AEs, and Serious AEs, by CTCAE (v.5.0). Vital signs (heart rate and blood pressure) Patient-reported outcome: challenging experiences (CEQ) 	 Day -28 through Day 35. Day 0 (multiple time points on day of ketamine administratio n). Day 0, 3-4 hours after ketamine administratio n.
2.	To assess the magnitude and durability of improvement from randomization in psychosocial distress.	 Clinician-rated outcomes: Global clinical impression of severity(CGI-S), Demoralization (DI), Mood symptoms (GRID-HAMD-6). Patient-reported outcomes: Demoralization (DS-II), Depression (PHQ9), Anxiety (GAD7), Quality of Life (FACIT-PaI-14). 	From Day -28 to Day 35.
3.	To assess the magnitude and durability of improvement from randomization in pain.	Patient-reported outcome: pain (BPI-SF)	From Day -28 to Day 35.
4.	To assess the magnitude of change from randomization in opioid analgesic use.	Patient-reported outcome: Opioid use (<24hr morphine milligram equivalence [MME])	From Day -28 to Day 35.
5.	To assess the magnitude of change from randomization in interoceptive awareness.	Patient-reported outcome: interoceptive awareness (MAIA-2)	From Day 0 to Day 7

Pilot Study - Ketamine Page 16 of 55

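### Section 9.2.3 states improvement from randomization but measures per-arm trends from the Visit 1 entry score; its DS-II cut-off also differs from the rest of the protocol

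*Combined protocol and SAP*

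**What the plan says.** The Abstract and section 2.3 give the objective as "To assess the magnitude and durability of improvement from randomization in psychosocial distress". Section 2.1 hypothesizes "improvements from randomization in measures of psychosocial distress, pain, opioid analgesic use, and interoceptive awareness", and section 9.2.3 (Secondary Objective #2) repeats "improvement from randomization in psychosocial distress associated with K-MaP". Sections 3.1 and 3.8 place randomization on Day 0, after two MaP sessions.

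The analysis text in 9.2.3 then measures mean trends in DS-II, PHQ-9, GAD-7 and FACIT-Pal-14 "in each study arm from baseline visit (Day -28 to -7) to post-ketamine (on Days 7, 14, and 35"). BPI-SF and opioid use (MME) are handled by analogy with DS-II. The between-arm ANCOVA is "adjusted for endpoints at baseline and randomization". Missing values are filled by "single imputation with baseline observations carried forward". The time frame in section 2.3 for these outcomes is "From Day -28 to Day 35".

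Section 9.2.3 also reports the proportion who "no longer meet criteria for moderate-to-severe demoralization (i.e., DS-II > 10) post-ketamine". The Abstract, section 3.1 and inclusion criterion 7 in section 3.3.1 all set moderate-to-severe demoralization at a score of 10 or higher.

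Section 9.1.1 says that a dose without treatment-related SAEs and with mean DS-II improvement lasting beyond 7 days would suggest a fully powered study. A well-tolerated dose without such improvement would be a suitable control. It names neither a reference visit nor a size. The Abstract gives a 2-point minimum.

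**The concern.** Baseline and randomization are different time points in this protocol. Section 6 schedules the patient-reported outcomes at each of them, and the ANCOVA uses both. For interoceptive awareness (MAIA-2), 9.2.3 does start at Day 0. The DS-II group of outcomes is therefore measured from a different point than its objective states.

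Two things can lower the score between Visit 1 and Day 0 with no contribution from ketamine. Participants are admitted because they scored 10 or higher, so some regression is expected. They also receive two MaP sessions. The stability rule (two qualifying scores at least 7 days apart) reduces the regression but does not remove it.

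At stake is the reading of the pilot. If the Visit 1 trend is used for 9.1.1, part of the improvement credited to a dose can arise before dosing, and a dose that belongs in the control branch could look promising. The cut-off matters on its own: with the sign as printed, an unchanged score of 10 counts as resolved, and so does a missing value filled with a baseline of 10.

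**Working it through.** The plan gives no power calculation, DS-II standard deviation or reliability, so it has no figure to reproduce. The textual mismatch stands without arithmetic. The numbers below only show its possible size.

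**Inputs.** From the documents: entry requires two scores of 10 or higher; scale 0-32; 6 per arm; 2-point minimum (Abstract). Assumed, not in the documents: DS-II mean 8-12 and SD 5-6 among referred patients, retest reliability r 0.6-0.9, no effect of therapy or drug. It is also assumed that the 2-point minimum applies to 9.1.1, and that lasting beyond 7 days means a 2-point fall at both Day 14 and Day 35.

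**Expected fall by regression alone.** With m the mean Visit 1 score of those admitted and μ the referred mean, selection on two equally reliable scores gives approximately

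fall = (1 − r)/(1 + r) × (m − μ)

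- μ = 8, SD 6, r = 0.6, simulated m = 14.47: 0.4/1.6 × 6.47 = 1.62
- μ = 10, SD 6, r = 0.6, simulated m = 15.12: 0.4/1.6 × 5.12 = 1.28
- μ = 12, SD 5, r = 0.9, simulated m = 14.91: 0.1/1.9 × 2.91 = 0.15

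Simulation over 24 combinations of mean, SD and reliability (scores rounded and limited to 0-32) agrees:

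| Quantity, no treatment effect | From Visit 1 | From Visit 4 |
|---|---|---|
| Mean fall, points | 0.16-1.63 | about 0 |
| Mean fall of at least 2 in an arm of 6, one visit | 3-44% | 2-19% |
| Same, at both Day 14 and Day 35 | 0.5-26% | 0.3-8% |

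Reliability drives the range. At r = 0.9 both figures in the last row are below 2%. The last row is closer to 9.1.1, because that section asks for improvement that lasts. The near-zero fall from Visit 4 follows from simulating no effect; it does not show that Visit 4 isolates the drug.

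**Cut-off.** One participant in an arm of 6 is 1/6 = 16.7 percentage points. In the same simulations 4.67-9.01% of follow-up scores are exactly 10. The chance of at least one such score among 12 at a given visit is 1 − (1 − 0.0467)^12 = 44% to 1 − (1 − 0.0901)^12 = 68%. With no treatment effect, 5-26% of participants would already be below 10 on Day 0.

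**Carry-forward.** Filling with Visit 1 is consistent with a Visit 1 reference. If the reference became Visit 4 and Visit 1 were still carried forward, an assumed 20% missing would add between 0.20 × 0.16 = 0.03 and 0.20 × 1.63 = 0.33 point of false worsening.

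**The case against.** The strongest defence is that the intervention is the K-MaP package, whose first two sessions precede Day 0. The time frame in section 2.3 starts at Day -28 for these outcomes and at Day 0 for MAIA-2, which looks deliberate. This stands as a defence of showing a Visit 1 trend. It does not make that trend a change from randomization, so either the analysis or the wording must move.

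A reader might infer that 9.1.1 will be decided on the Visit 1 trend. The text does not say so. It speaks of improvement shown by a dose and lasting after the drug, for which Day 0 is a natural reading. The supportable statement is that the reference is not named.

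A reader might also infer that no per-arm display uses the Day 0 score. That is too strong: 9.2.3 also plots ANCOVA mean trends per arm, from models adjusted for both scores. The Visit 1 trend is the one whose starting point is written out.

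Nor is Visit 4 a clean drug reference. Two MaP sessions follow ketamine, both arms receive ketamine, and the 2-week DS-II recall means that a Day 7 score reaches back to about Day -7.

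Finally, the printed cut-off may be a slip or a lost mark in the PDF. The greater-or-equal sign survives in sections 3.1 and 3.3.1, which makes a reading error less likely, but the original should be checked.

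**Conclusion.** The mismatch is real and should be fixed. For six patient-reported outcomes, the per-arm trend defined in 9.2.3 does not measure what the objective states, and followed as written it credits pre-ketamine change to improvement from randomization. The cut-off in 9.2.3 contradicts three other places and, read literally, can only raise the resolved proportion. Confidence in both textual points is high.

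The size is uncertain. The excess fall of 0.2-1.6 points, set against a 2-point minimum, rests wholly on the assumed mean, SD and reliability, and is small if reliability is near 0.9. An effect on the next-trial decision is conditional on how 9.1.1 is applied. The comparison between arms is not put in doubt by this point. The analysis is secondary and descriptive, there are no formal efficacy tests, and 9.1.1 also requires zero treatment-related SAEs, so the harm is to interpretation.

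**What to change.** 1. In 9.2.3, report per-arm change in DS-II, PHQ-9, GAD-7, FACIT-Pal-14, BPI-SF and MME from the pre-dose Visit 4 value, and show Visit 1 to Visit 4 separately. If the whole-package trend is meant, change the objective to improvement from baseline for these outcomes in the Abstract and sections 2.1, 2.3 and 9.2.3.
2. In 9.1.1, use change from Visit 4 for the per-dose statement. If Visit 1 is kept, say that the improvement is that of the K-MaP package and show the pre-ketamine part beside it. In either case, state that change from Visit 4 still includes two MaP sessions and does not isolate ketamine.
3. After checking the sign in the original PDF, write the criterion as DS-II ≥ 10, with resolved meaning below 10, and show the Day 0 proportion below 10 next to the later ones.
4. If Visit 4 becomes the reference, carry the Visit 4 value forward for missing post-ketamine data.
5. Extend Visit 4 to CGI-S, DI and GRID-HAMD-6 only once section 6, which schedules them immediately before randomization, is reconciled with the section 6.1 calendar, which appears to mark only Visits 1, 8 and 9.

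The cost for the six patient-reported outcomes is wording: section 6 and the calendar already collect them at Visit 4 before dosing. The downside is a smaller apparent improvement and a lower resolved proportion.
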